4 STUDY DESIGN

4.1 OVERALL DESIGN

Connect-Home is a stepped-wedge cluster randomized trial (SW-CRT) to test the Connect-Home intervention against standard discharge planning (control), using both patients discharged to home (N=360) and their caregivers (N=360) in 6 SNFs.⁴⁴ In this design, SNFs will be randomly allocated to one of six sequences of time-periods defined by the month at which a SNF begins the control condition and, after a two-month staff training period, the time-period (or "step") that begins the Connect-Home protocol condition (Figure 2).⁴⁵ Thus, all SNFs will contribute data for both the Connect-Home intervention and standard care in a uni-directional crossover design at the cluster (SNF) level; a patient and their caregiver receives either standard discharge planning or Connect-Home consistent with the treatment condition of the SNF at the time of the patient's enrollment.

Randomization will be conducted for all sites simultaneously by a study statistician blinded to SNF identity. The randomized allocation sequence of the SNF will determine the beginning and end dates for three phases of patient and caregiver enrollment: (1) standard care, (2) the pre-implementation phase when staff are trained and neither patients nor caregivers are enrolled, and (3) the implementation phase when newly enrolled patients and their caregivers receive Connect-Home.

Patients and caregivers will be enrolled on a rolling basis at the rate of 4-5 dyads per month anytime during the control or intervention period. There will be three phases of patient and caregiver enrollment: (1) standard of care (indicated by blue boxes in Figure 2), (2) the pre-implementation phase when staff are trained and neither patients nor caregivers are enrolled (indicated by orange boxes in Figure 2), and (3) the implementation phase when newly enrolled patients and their caregivers receive the Connect-Home intervention (indicated by green boxes in Figure 2).

Figure 2. Stepped Wedge Design with treatment condition by month for 6 SNFs enrolling 4 patients and their caregivers per month (N= 360 patients and 360 caregivers)

SNF	Period = 1 month																					
	1	2	3	4	5	6	7	8	9	10	11	12	13	14	15	16	17	18	19	20	21	22
1	4	4	4	4	4			4	4	4	4	4	4	4	4	4						
2		4	4	4	4	4	4			4	4	4	4	4	4	4	4	4				
3			4	4	4	4	4	4	4			4	4	4	4	4	4	4	4	4		
4				4	4	4	4	4	4	4	4			4	4	4	4	4	4	4	4	
5					4	4	4	4	4	4	4	4	4			4	4	4	4	4	4	4
6						4	4	4	4	4	4	4	4	4	4			4	4	4	4	4

The primary objectives will be assessed 7 days after discharge. The secondary and exploratory outcomes will be assessed 30 and 60 days after discharge.

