5.4 STRATEGIES FOR RECRUITMENT AND RETENTION

Recruitment:

The study team will obtain a limited waiver of HIPAA authorization to allow pre-screening for patient eligibility. The team will consult at least weekly with the Minimum Data Set Nurse, social worker, or other personnel involved in coordinating clinical care for newly admitted patients in each SNF by phone, email, or in-person to identify patients that are expected to be discharged from the SNF to home, and subsequently screen the medical records of all patients expected to discharge from the SNF to home.

After identifying potentially eligible patients, the study team will recruit SNF patients and their caregivers in-person (or, when risk mitigation related to COVID-19 prevents in-person contact, we will recruit virtually, using an iPad and connection via ZOOM) within 10 days of their admission and will review the patient's medical record to confirm eligibility. For patients with cognitive impairment, the team will recruit the patient's legally authorized representative to respond to survey questions as the patient's proxy.

Recruitment will be conducted in the SNFs through in-person interactions (or, when risk mitigation related to COVID-19 prevents in-person contact, we will recruit virtually, using an iPad and connection via ZOOM). If necessary, recruitment can also be conducted by telephone for caregivers. All participants will provide written informed consent (or, when risk mitigation related to COVID-19 prevents in-person contact, we will obtain consent verbally using an iPad and connection via ZOOM) for study participation. When written consent is not feasible, we will obtain witnessed verbal consent with the assistance of nursing home personnel via the iPad and Zoom connection). Legally authorized representatives will give consent for patients with cognitive impairment. Consent and HIPAA Authorization could also be obtained verbally in the situation that a participant is unable to physically sign these documents.

Retention:

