6.3 STUDY INTERVENTION COMPLIANCE

The NIH Behavior Change Consortium's "Treatment Fidelity Protocols" will be used to ensure fidelity to the intervention.⁴⁶ Fidelity will be assessed in five domains as described below.

Design: The researchers will use standardized tools (e.g., Connect-Home Toolkit, the EHR template and staff training protocols) to deliver the intervention.

Training: To prevent contamination between SNFs during the intervention phase, the researcher will train staff in individual SNFs and Connect-Home Activation RNs in individual home health care offices. A detailed training protocol will be used, specifying the researcher roles, content, participants, and time required for training activities.

Delivery: A researcher will observe staff training activities on a random schedule to assess fidelity of the trainer to the staff training protocols. The research team will develop plans to address deviations from the training protocol. A Training Contact Database will be used, in which researchers will record staff participation in training activities. Staff members will be assigned identification numbers for tracking participation.

Receipt of Treatment: Researchers will administer post-tests to all participating staff after the staff training session; additional one-to-one re-training will be provided as needed for those who score

<100%. Researchers will also use return demonstration of home visit procedures with Connect-Home Activation RNs, followed by re-training as needed until nurses demonstrate a high level of ability.

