9.3 POPULATIONS FOR ANALYSES

An intent to treat analysis will be used in which all patients/caregivers are included in the analysis according to their treatment allocation at enrollment, regardless of whether they receive the full intervention.

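### The last control dyads in each SNF may still be in the facility when Connect-Home staff training starts, which may dilute the primary effect; the plan neither prevents nor examines this

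*Combined protocol and SAP*

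**What the plan says.** Section 4.1 assigns each dyad to the condition of its SNF on the enrollment date: "a patient and their caregiver receives either standard discharge planning or Connect-Home consistent with the treatment condition of the SNF at the time" of enrollment. Section 9.3 analyses dyads on the same basis, "according to their treatment allocation at enrollment, regardless of whether they receive the full intervention". Dyads enter "at the rate of 4-5 dyads per month anytime during the control or intervention period", and Figure 2 shows full enrollment in every SNF's last control month.

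The next two months are "the pre-implementation phase when staff are trained and neither patients nor caregivers are enrolled". That stops new entries. It says nothing about control patients already enrolled and still in the facility.

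Under Section 5.4, patients are recruited "within 10 days of their admission". Table 1 (Section 6.1.1) places the last in-SNF step on days 6-20 and the home visit on day 21.

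Two safeguards against contamination are described. Section 4.2 relies on randomizing whole SNFs. Section 6.3 is aimed at spread between facilities: "To prevent contamination between SNFs during the intervention phase, the researcher will train staff in individual SNFs". The only sensitivity analysis on implementation timing (Section 9.4.2) divides the intervention period at three months.

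**The concern.** The social workers, nurses and rehabilitation therapists who are trained are the people who prepare patients for discharge, and preparedness is what the CTM-15 measures. A control patient enrolled near the end of the last control month could be taught and discharged after some of those staff have attended Connect-Home sessions. Section 9.4.2 itself places the first implementation of Connect-Home in the training period, so some early change in practice is plausible.

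Any such exposure moves control outcomes toward intervention outcomes and biases the effect toward the null. All the exposed dyads fall in the month next to the crossover. Once the model adjusts for time, the comparison leans heavily on that month. The same mechanism applies to the caregiver co-primary outcome, for which Section 9.2 gives no separate power figure.

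**Working it through.** **Inputs.** Section 9.2: effect 0.15 on log CTM-15, 277 evaluable patients, 89% power, two-sided 5% test, within-period ICC 0.10, between-period ICC 0.05, 23% dropout. Section 9.4.2: linear time trend, random effects for SNF and for period within SNF. Figure 2: 45 control and 47 intervention SNF-months at 4 dyads each. Control dyads: 45 × 4 = 180. As extracted, the figure totals 92 × 4 = 368 dyads against the stated 360; this may come from the text extraction and does not affect the argument.

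**The plan's own figures.** 360 × 0.77 = 277.2 and exp(0.15) − 1 = 16.2%, both as stated. The 89% cannot be reproduced because no SD for log CTM-15 is given. I set the standard error to the value that yields 89%: 0.15 / (1.960 + 1.227) = 0.047. This implies an SD of 0.194 under the linear trend.

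**Number of dyads.** Remaining stay at enrollment: 20 − 10 = 10 days to 20 − 1 = 19 days. Per SNF: 4 × 10/30 = 1.3 to 4 × 19/30 = 2.5. Over six SNFs: 8 to 15 dyads, or 4.4% to 8.4% of 180. At 5 per month the upper figure is 6 × 5 × 19/30 = 19. After 23% dropout, about 6-12 of the 8-15 would be evaluable.

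**Weight of the last control month.** Generalized least squares on the Figure 2 layout, with the plan's ICCs and 277 patients spread evenly over the SNF-months, gives the weight of each SNF-month in the treatment estimate. The six last-control months are 6/45 = 13% of control SNF-months but carry 38% of the net control-side weight under the linear trend.

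**Dilution.** Let f be the share of the effect that an exposed control dyad receives.

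- Expected estimate / true effect = 1 − 0.38 × (days/30) × f
- Power = Φ(expected estimate / 0.047 − 1.960)

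For example, with 19 days and f = 0.5: 1 − 0.38 × 0.633 × 0.5 = 0.88. The expected estimate is 0.132 and power is 80%.

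| f (assumed) | Ratio, 10 to 19 days | Expected estimate | Power |
|---|---|---|---|
| 0.25 | 0.97 to 0.94 | 0.145 to 0.141 | 87% to 85% |
| 0.50 | 0.94 to 0.88 | 0.141 to 0.132 | 85% to 80% |
| 1.00 (ceiling) | 0.87 to 0.76 | 0.131 to 0.114 | 79% to 68% |

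Months fitted as categories give nearly the same result (f = 0.5: power 85% to 81%). With no time trend, attenuation is 1-4% for f = 0.25-0.5 and at most about 9% at f = 1.

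**The case against.** A reader might infer that the last control patients are in fact taught by trained staff, that the effect is diluted as a matter of course, and that power falls below 70%. The documents do not support that, for four reasons.

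- **Training is not dated.** The overlap covers only the first 10-19 days of about two months. Section 6.1.1 lists training of project leaders separately from staff training and has staff adopt the new processes once the organizational elements are in place. If front-line sessions come later, there is no contamination.
- **The 10-19 days is an inference.** It comes from the nominal Connect-Home schedule. No length of stay is given for control patients, and shorter stays fit the same row of Table 1.
- **Full contamination is a ceiling.** Control dyads get no Activation RN home visit. Only those enrolled on the last control day spend the whole remaining stay in the training phase; average overlap is about half of that.
- **The EHR template is not evidence here.** It is installed before randomization, so it is present in every control month and cannot explain a change confined to the last one.

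The share of dyads is also small, and the bias runs toward the null, so it would not create a false positive. All of this stands and limits the claim to a possible dilution of modest size. It does not remove the point: nothing in the plan rules the overlap out, and no planned analysis would show it.

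**Conclusion.** The point holds as a conditional risk. Allocation by enrollment date, full enrollment up to the training phase, and the lack of any rule on within-SNF carry-over are all in the protocol. That dilution will occur is not.

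If the 8-15 overlapping control dyads receive 25-50% of the effect, the expected estimate loses about 3-12% and power is about 87-80% rather than 89%. This rests on four assumptions: a stay of about 20 days, front-line training early in the two months, the assumed value of f, and a standard error calibrated to the stated power. The planned trend term is what lifts the loss above the dyads' raw 4-8% share when exposure is strong. The fix is cheap enough to be worth making even though the exposure is uncertain.

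**What to change.** **Section 9.4.2.** Pre-specify a sensitivity analysis for both primary outcomes that excludes control dyads discharged after their SNF's first front-line staff training date, and record that date for each SNF. SNF length of stay is already abstracted; the discharge date must be available to compare with the training date. The analysis by condition at enrollment stays primary, because the exclusion selects on an event after enrollment. Cost: if all 8-15 dyads are dropped, power in that analysis is about 87-86% under the linear trend.

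**Sections 4.1 and 6.1.1.** State that, where feasible within the existing two-month gap, front-line training sessions in a SNF are held after its last enrolled control dyad has been discharged. Leadership training can go ahead earlier. Cost: a shorter window for front-line training, with no loss of dyads. How much shorter depends on control length of stay, which the documents do not give.

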4.2 SCIENTIFIC RATIONALE FOR STUDY DESIGN

The study will utilize a SW-CRT, as it retains statistical power to evaluate efficacy of the intervention on the primary outcome in a relatively small number of SNFs. Observing SNF's under standard practice followed by the Connect-Home intervention is also consistent with the actual practice of implementing organizational change in SNFs and provides opportunities for evaluating implementation procedures. Cluster randomization at the nursing home level reduces risk of contamination between control and Connect-Home participants (Figure 2).

4.3 END OF STUDY DEFINITION

The end of study will be when the study team completes the final enrolled participant's 60-day assessments, and all data (including the final home health care chart reviews) have been collected from all study subjects. If a subject is withdrawn from the study due to an early termination caused by hospitalization, SNF re-admission and/or death; end of study for these patients will occur on day of early termination.

5 STUDY POPULATION

5.1 INCLUSION CRITERIA

Patients must satisfy all the following inclusion criteria prior to being enrolled:

1. English-speaking;
2. Have a Minimum Data Set 3.0, Section GG Mobility Assessment Score of 3 or less, indicating the patient requires at least 25-50% assistance for functional mobility;
3. Diagnosed with at least 1 serious medical illness (neurodegenerative dementia, cancer, chronic kidney disease, cirrhosis, congestive heart failure, chronic obstructive or interstitial lung disease, acute infection with sepsis, acute major motor stroke, acute coronary syndrome, acute hip fracture, diabetes with end organ complications, or intensive care for > 3 days while hospitalized);
4. Have a caregiver who can be enrolled in the study.

For patients with cognitive impairment, (defined as documented diagnosis of dementia and/or a Brief Interview for Mental Status score of ≤ 12 in Section C of the Minimum Data Set) additional criteria include:

1. Documentation in the medical record of a caregiver who is the patient's legally authorized representative;
2. Consent of the caregiver to participate in the study as the patient's representative.

Caregivers must satisfy all of the following inclusion criteria prior to being enrolled:

1. Must self-report assisting the patient at home;
2. English-speaking.

5.2 EXCLUSION CRITERIA

Patients will not be entered into Connect-Home if the criterion below is satisfied:

1. Planned hospital readmission for procedures or treatments within 90 days post enrollment.

Caregivers in the study have no noted exclusion criteria.

5.3 SCREEN FAILURES

Subjects who discontinue following consent (i.e., post in-person questionnaires at recruitment) but prior to receiving the Connect-Home intervention or control will be considered screen failures. No additional data will be collected from the time of screen failure, but data collected prior to screen failure and reason for screen failure will be kept.

5.4 STRATEGIES FOR RECRUITMENT AND RETENTION

Recruitment:

The study team will obtain a limited waiver of HIPAA authorization to allow pre-screening for patient eligibility. The team will consult at least weekly with the Minimum Data Set Nurse, social worker, or other personnel involved in coordinating clinical care for newly admitted patients in each SNF by phone, email, or in-person to identify patients that are expected to be discharged from the SNF to home, and subsequently screen the medical records of all patients expected to discharge from the SNF to home.

After identifying potentially eligible patients, the study team will recruit SNF patients and their caregivers in-person (or, when risk mitigation related to COVID-19 prevents in-person contact, we will recruit virtually, using an iPad and connection via ZOOM) within 10 days of their admission and will review the patient's medical record to confirm eligibility. For patients with cognitive impairment, the team will recruit the patient's legally authorized representative to respond to survey questions as the patient's proxy.

Recruitment will be conducted in the SNFs through in-person interactions (or, when risk mitigation related to COVID-19 prevents in-person contact, we will recruit virtually, using an iPad and connection via ZOOM). If necessary, recruitment can also be conducted by telephone for caregivers. All participants will provide written informed consent (or, when risk mitigation related to COVID-19 prevents in-person contact, we will obtain consent verbally using an iPad and connection via ZOOM) for study participation. When written consent is not feasible, we will obtain witnessed verbal consent with the assistance of nursing home personnel via the iPad and Zoom connection). Legally authorized representatives will give consent for patients with cognitive impairment. Consent and HIPAA Authorization could also be obtained verbally in the situation that a participant is unable to physically sign these documents.

Retention:

During recruitment, study personnel will give the patient and caregiver a study flyer providing the study team's contact information, a schedule of planned follow-up calls, and information regarding compensation for completing data collection. When study personnel is unable to provide these study flyers directly to the patient, the study team will provide flyers to NH staff to announce the study and the possibility that a study team member will speak with potential study participants in-person or

virtually (using an iPad) about participating in the study. The study team will also mail reminder letters to patients and caregivers one week before 30 and 60-day data collection calls

The study team will also continuously monitor retention throughout the study. If retention falls below the anticipated rate, study personnel will further emphasize data collection in recruitment and will send additional written reminders to participants.

6 STUDY INTERVENTION

6.1 STUDY INTERVENTION(S) ADMINISTRATION

6.1.1 STUDY INTERVENTION DESCRIPTION

The Connect-Home intervention will introduce new organizational structure to support staff delivery of transitional care processes for seriously ill patients being discharged from the SNF to home.²⁷ New elements of organization structure in the Connect-Home intervention include:

- The "Transition Plan of Care Template" EHR tool, to be installed in the SNF EHR system prior to randomization. It contains domains that SNF staff and home visit RNs use to record and deliver the two-step Connect-Home intervention.²⁷
- The "Connect-Home Toolkit", a bound workbook that contains a description of the EHR template and other EHR tools, the two-step Connect-Home intervention protocol, checklists and cue sheets, and the intervention schedule.²⁷
- Site leadership training, where the Investigator trains 1-5 SNF project leaders on the Connect-Home protocol and study procedures.
- Executive sponsor and QI nurse monthly calls during intervention phase
- Monthly accountability calls with QI nurses and individual facilities to maintain accountability to protocol
- Staff Training, where the Investigator will train social workers, nurses, rehabilitation therapists, and the Connect-Home Activation RN on patient and caregiver key care needs, protocols for using the two-step intervention to address patient's key care needs, using the "Transition Plan of Care Template" EHR tool, advance care planning, and integrating SNF-based and home-based care.²⁷ The training will also include American Geriatrics Society recommendations for self-care at home in the context of the COVID-19 pandemic (when applicable).
- Focused training for the Connect-Home Activation RN, where the Investigator will train the Connect-Home activation RN on strategies for implementing transition plans of care, home safety screening, responding to medical needs, and handing off care to home health nurses.

After these elements of organizational structure are in place, the SNF staff will use the Connect-Home intervention care processes to deliver the 2-step transitional care intervention.²⁷ Further details are provided in Table 1.

- In Step 1, SNF nurses, rehabilitation therapists, and social workers will develop a Transition Plan of Care and prepare the patient and caregiver to manage the patient's serious illness and functional needs at home. Staff also will use American Geriatrics Society recommendations for self-care at home in the context of the COVID-19 pandemic (when applicable).

- In Step 2, the Connect-Home Activation RN (employed in the collaborating home health agency) will visit the patient and caregiver at home within 24 hours of discharge; the nurse will work with them to activate the Transition Plan of Care at home. Nurses also will use American geriatrics Society recommendations for self-care at home in the context of the COVID-19 pandemic (when applicable).

Process	Patient/Caregiver Services and Supports	Day
Step 1. Transitional care in the SNF ²⁷	
Set goals for home-based care (45 minutes)
 
Consulting with the patient/caregiver, SNF staff use the EHR template to describe goals in the patient’s Transition Plan of Care, targeting 6 key care needs (home safety and level of assistance, advance care planning, symptom management, medication reconciliation, function and activity and coordination of follow-up medical care). Staff will use American Geriatrics Society recommendations for self-care at home in the context of the COVID-19 pandemic (when applicable).
 
 • Nurses create goals for planned treatments at home, and responses to emerging symptoms or other health changes at home • Rehabilitation therapists create goals for mobility, transfers and self-care at home. • Social worker creates goals for caregiver support, follow-up care & discharge disposition. 	2 - 17
	
Meet to plan the patient’s transition to home-based care (30 minutes)
 
In dialogue with the patient/caregiver, the treating nurse, social worker and therapists will develop a plan for home-based care, targeting 6 key care needs (home safety and level of assistance, advance care planning, symptom management, medication reconciliation, function and activity, and coordinator of care).
 
 • Nurses focus on medications, elements of advance care planning and symptom management. • All staff help the patient and caregiver describe their needs for continuing medical, supportive and rehabilitative care at home. • Social worker reviews participation in Connect-Home, including the Transition Plan of Care and the Connect-Home Activation RN Visit. 	5 - 10

	
Prepare the patient and caregiver for home-based care (2.5 hours)
 
1. Teach skills and plans for home-based care, targeting 6 key care needs (home safety and level of assistance, advance care planning, symptom management, medication reconciliation, function and activity, and coordinator of care). Staff will use American Geriatrics Society recommendations for self-care at home in the context of the COVID-19 pandemic (when applicable).
 
 • Nurses teach symptom management (e.g., pain), clarify advance care planning preferences, and reconcile medication orders • Rehabilitation Therapists teach skills for function, safety and continuing rehabilitation at home. • Social worker schedules and explains appointments, home-based care & cost 
2. Initiate hand-off to home-based care (over the last 1-2 days before discharge)
 
 • SNF staff send medical records and copies of any advance care planning documents to the patient’s physician and the Connect-Home Activation RN • Nurses: 1) reconcile medications, 2) provide supplies and medications, and 3) re-teach the written Transition Plan of Care and medication list. • Social Worker coordinates the hand-off of care to the Connect-Home Activation Nurse. 	
6 - 20


Step 2. Transitional care in the patient’s home
	
Implement the Transition Plan of Care at home (2 hours)
 
Connect-Home Activation Nurse visits the patient and caregiver at home to:
 
 • Reconcile medications on the discharge medication list and in the home, • Reviews TPOC and adds materials for patient care as needed • Help family implement new care routines, addressing 6 key care needs (home safety and level of assistance, advance care planning, symptom management, medication reconciliation, function and activity, and coordinator of care). • Conduct a brief home safety & falls prevention screen, and • Coordinate care and communicate the plan of care to follow-up clinicians and home health care nurses, and others as applicable. Nurses will use American Geriatrics Society recommendations for self-care at home in the context of the COVID-19 pandemic (when applicable). 	
21

